Including determination of working length, degree of foraminal enlargement, number of visits, analgesics consumption, gender ⁽²⁻⁵⁾, technique of filing and instrumentation system, kinematics, trauma of periapical tissue or bacterial extrusion and root canal sealer. specifically, extrusion of root canal sealer can disrupt periodontal tissues and cause inflammatory reactions. The intensity of this reaction depends on the composition of the sealer.

Different types of sealers can be used during obturation of root canals like zinc oxide and eugenol sealers, resin sealers or bio ceramic sealers. Resin sealers maybe epoxy, or methacrylate based, they are radiopaque, have low solubility and are biocompatible and have good flow while bio ceramic sealers contain alumina, zirconia particles, bioactive glass, calcium silicates, hydroxyapatite, and resorbable calcium phosphates ⁽⁶⁾. These ingredients allow the sealers to resist bacterial leakage, rendering it biocompatible, simulating dynamic intratubular biomineralization. Bioceramic sealers release bioactive substances and enhance endodontic treatment outcomes by facilitating the differentiation of odontoblasts. However, resin sealers show higher bonding strength and radiopacity compared to bioceramic sealers.

Bioceramic sealers were introduced into the market as to cause less post operative pain after obturation compared to other sealers that is why studies were conducted to validate this fact with evidence.

The null hypothesis is that there is no difference in post operative pain between resin and bio ceramic sealers after endodontic treatment.

Review of Literature

Postoperative pain is defined as pain of any degree after initiation of root canal treatment either intra-appointment or post-obturation and is considered an undesirable occurrence for both patient and clinician.⁽⁷⁾

After cleaning and shaping of the canals Obturation can be performed using different types of sealers.

- Resin sealers are classified to epoxy resin based or methacrylate-based resin sealers. Epoxy resin-based sealers are commonly used due to their low solubility, micro-retention to dentin of root canal and their good apical seal. Currently modifications of the original formula are used widely⁽⁸⁾. Epoxy resin-based sealers are characterized by the reactive epoxide ring and are polymerized by these rings.

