- Bio ceramic sealers are sealers that contain **calcium silicate and/or calcium phosphate** as their main compositions. Bioactive materials, such as glass and calcium phosphate, interact with the surrounding tissue to encourage the growth of more durable tissues⁽⁹⁾, it can penetrate the dentinal tubules and interact with dentine moisture to create bonds between the dentin and core filling materials, an optimum dimensional stability, and the least amount of shrinkage.
(10)

Pain is evaluated using visual analogue scale (VAS)⁽¹¹⁾

- It is a pain rating scale. Scores are based on measures that are self-reported of symptoms that are recorded through a single handwritten mark placed at one point along the length of a 10-cm line representing a continuum between the two ends of the scale— on the left end of the scale (0 cm) means “no pain “and the on the right end of the scale (10 cm) “worst pain “

Pak and White ⁽¹²⁾conducted a systematic review to assess the prevalence and severity of pretreatment, treatment, and post-treatment pain in patients receiving root canal treatment. They reviewed 72 studies for meta-analysis and concluded that pretreatment endodontic pain of high intensity dropped moderately within 1 day reaching minimal levels after 7 days & post-treatment pain prevalence was moderate or low stating that most included articles reported 7-day pain relief as the severity starts to drop from the first day till less than 10% after 7 days.

Ali et al., ⁽¹³⁾investigated the prevalence of post-operative pain after single visit endodontic treatment in the Indian population using protaper rotary files in addition to hand instruments by evaluating the factors that might affect pain experience. Their study included One thousand three hundred and twenty-eight patients. post-operative pain was evaluated using visual analogue scale by each patient by well-defined categories at three-time intervals, 12, 24, and 48 hours. They concluded that the prevalence of post operative pain was low (4%) and the important prognostic determinants of post-operative pain were presence of pre-operative pain, old age, gender (females recorded higher), and mandibular teeth but the vitality of the tooth had no effect on the intensity nor the frequency of post operative pain.

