Ferriera et al., ⁽²⁰⁾ compared the occurrence and intensity of postoperative pain and analgesic intake after root canal treatment, using different root canal sealers on sixty single rooted necrotic asymptomatic teeth with apical periodontitis dividing the sample to three groups according to the type of sealer used for obturation(AH Plus, Endofill or MTA Fillapex). Endodontic treatment was performed in two visits with placing calcium hydroxide dressing as intra canal medicament inter appointment . In terms of either incidence or intensity of postoperative pain or need for analgesic intake no significant differences were detected among the groups, at any timepoint. No pain was reported after 7 days. AH Plus, Endofill and MTA Fillapex used for filling root canals resulted in the same rate of postoperative pain and need for analgesic medication.

Shim et al., ⁽²¹⁾ compared the effects of bio ceramic sealer and resin-based sealer on the incidence and intensity of postoperative pain on one hundred and eight patients with anteriors and premolars and molars requiring endodontic treatment. In groups En1(premolars or anteriors) and En2(molars), root canals were obturated with Endo seal MTA using the single-cone technique. In groups AH (premolars or anteriors) and AH2(molars), the sealer used was AH Plus with the continuous wave technique. Pain was assessed through visual analogue scale over 7 days period. They found that: Endo seal MTA and AH Plus had similar

effects on the incidence and intensity of postoperative pain. The obturation time was shorter when using Endo seal MTA compared to AH Plus.

PICO

P: patients diagnosed with irreversible pulpitis age from 18-50 years old

I: obturation with bioceramic sealer

C: obturation with resin sealer

O: effect on post operative pain

Aim of the study

The aim of this randomized clinical trial is to evaluate the post-operative pain after obturation using Resin Vs. Bioceramic sealers.

Participants and Methods

I-Materials

| |
|--------------------------------------|
| Round bur/endo Z/tapered round stone |
| Rubber dam |
| #10_k files |
| Apex locator |
| #15 #20_k files |
| Side vented needle |
| 5.25% sodium hypochlorite |
| Rotary files |
| Endo motor |
| Sensor |
| Paper points |
| Gutta percha points |
| Resin sealer |
| Bioceramic sealer |
| Torch |
| Condenser |
| Cotton and temporary filling |

II-participants

A-Sample size determination:

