Sample size calculation was performed using G power (3.1.9.4) software, based on a previous study ⁽²²⁾ using an alpha (α) level of 0.05 and beta (β) level of 0.85. The predicted sample size (n) is a total of 40.

B-Patient's selection:

1-Eligibility criteria:

Inclusion criteria:

- Patients age ranges from 18-50 years old.
- Patients with teeth diagnosed with symptomatic irreversible pulpitis.
- Normal periapical condition confirmed by normal periapical radiograph or that with minimal widening of the PDL space
 - The teeth are restorable
 - Teeth are periodontally free.

Exclusion criteria:

- Teeth with immature roots
- Non restorable teeth
- Medically compromised patients with systemic complication that would alter the treatment.
 - Necrotic teeth
 - Teeth with apical periodontitis or periapical lesions
 - Teeth that need multiple visits treatment

2-Ethical consideration:

Patient will be asked to follow general instructions and to sign a printed informed consent explaining the aim of study, brief of study methodology, benefits and complications of the procedure and requesting that they allow clinician to follow up after performing the treatment. This study will be performed in compliance with the ethical standards laid down in the 2013 Declaration of Helsinki

Adverse events during the trial will be reported to supervisor and co supervisor and monitors of ethical committee

C-Patient allocation:

Using computer generated randomization, the participants will be allocated randomly into two equal groups.

The sequentially numbers that will be generated, will be placed in opaque envelope until the intervention and each participant will be asked to select an envelope that determine which group of intervention he will be assigned.

D-Patient Classification:

Patients were randomly divided into two groups according to material used for obturation . each patients name will be replaced with a case number within the group to protect the privacy of medical information and data of the patients

Group (1) resin sealers

Group (2) bio ceramic sealer

Methods

Procedural steps:

- Pain scale chart will be given to each patient to rate his /her pain level before endodontic treatment as preoperative reading on a visual analogue scale (VAS)
 - Tooth will be anaesthetized using Local anesthesia containing Articaine with epinephrine 1:100,000.
 - Access cavity will be performed using a carbide round steel bur and tapered diamond stone until complete deroofing.

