 - Rubber dam isolation of tooth
 - Patency is gained and working length is recorded using apex locator and confirmatory radiograph.
 - Cleaning and shaping using rotary system
 - Irrigation using 5.25% sodium hypochlorite introduced using side vented needle
 - Activation of the irrigant
 - Master cone check
 - obturation
 - temporary restoration will be placed

Methods of evaluation

Post operative pain

Each patient will be asked to fill the visual analogue scale (figure 1) to rate the pain level postoperatively at 6, 24, 48, and 72 hours following the end of the procedure.

[figure not shown]

Figure 1: Visual analogue scale used by the patient to report pain level at different time intervals

G-Statistical analysis:

Data obtained will be tabulated in the form of groups and case numbers to protect patient's confidentiality.

Data will be statistically analyzed using non-parametric tests to compare numerical variables (age, VAS scores) amongst the groups. other test will be used to evaluate the changes in pain scores over time. Categorical variables (gender, type of teeth) will be compared amongst the groups . Also, the correlation assessments between age factor and postoperative pain, and gender factor and postoperative pain will be done.

References

4. Seymour, R.A. The use of pain scales in assessing the efficacy of analgesics in post-operative dental pain. *Eur. J. Clin. Pharm.* 1982, 23, 441–444
6. Savannah, G. Bioceramic technology—The game changer in endodontics. *J Endod. Pract.* 2009, 13, 13–17.

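### Pain is compared between sealers at four postoperative times, but the protocol names no time, summary or multiplicity rule that decides its single null hypothesis

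*Protocol*

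**What the plan says.** The hypothesis is single and general: "The null hypothesis is that there is no difference in post operative pain between resin and bio ceramic sealers after endodontic treatment". The PICO entry is equally general: "O: effect on post operative pain". Neither they nor the aim of the study mention a time.

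Under Methods of evaluation, patients "rate the pain level postoperatively at 6, 24, 48, and 72 hours following the end of the procedure". A preoperative VAS reading is also taken (Procedural steps), but its part in the comparison is not stated.

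Section G (Statistical analysis) has two sentences that bear on pain. The first covers the comparison between sealers: "Data will be statistically analyzed using non-parametric tests to compare numerical variables (age, VAS scores) amongst the groups". It singles out no reading. The second concerns the course of pain and adds only this: "other test will be used to evaluate the changes in pain scores over time".

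Section A (Sample size determination) gives an alpha of 0.05, a beta printed as 0.85, and this: "The predicted sample size (n) is a total of 40". Section C allocates patients to two equal groups, so 20 per group.

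No section names a primary time, a summary over time such as a peak, mean or area under the curve, a repeated-measures group effect as the deciding test, or a rule for combining four comparisons.

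**The concern.** One hypothesis with one alpha needs one deciding comparison, or a stated rule for several. Here four between-group comparisons of VAS are available and none is singled out. A result at 24 h alone, say, could be reported as a sealer difference or set aside as incidental, and the protocol would permit either.

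Two things are at stake. If the choice is made after the data are seen, the 5% error rate no longer describes the trial's conclusion. And the reader cannot tell which comparison the sample of 40 is meant to serve.

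**Working it through.** **Inputs from the protocol.** Four postoperative times; alpha 0.05; 20 per group; non-parametric between-group tests; 0.85 printed as beta.

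**Assumptions.** Tests are two-sided (the protocol does not say). The 0.85 is read as power. The correlation between a patient's readings is not given, so a range is shown.

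**1. The protocol's own figure.** The total of 40 cannot be rebuilt, because no outcome time, effect size, SD or test is given. It can be turned round to ask what standardised difference d it detects at a single comparison:
- Normal approximation: d = (z₀.₉₇₅ + z₀.₈₅) / √(n/2) = (1.960 + 1.036) / √10 = 0.948.
- Two-sample t-test (noncentral t, 20 per group): d = 0.972.
- Rank test, with efficiency 0.955 relative to the t-test (20 × 0.955 = 19.1 effective per group): d = 0.996, about 1.0 SD.

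**2. False-positive rate if any of the four times may count.** With independent tests: 1 − (1 − 0.05)⁴ = 1 − 0.8145 = 0.1855, or 18.5%.

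Readings from one patient are correlated, which lowers this. The rates below are simulated with no sealer effect and equal correlation between all times. The Mann-Whitney column uses 20 per group and 20,000 trials; the normal column uses 1,000,000 draws of the test statistics.

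| Assumed correlation | Mann-Whitney | Normal statistics |
|---|---|---|
| 0.3 | 17.3% | 17.4% |
| 0.5 | 15.6% | 15.6% |
| 0.7 | 13.2% | 13.0% |
| 0.9 | 9.9% | 9.4% |

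With correlation that fades as the times move apart (first-order autoregressive), the Mann-Whitney rates at 0.5, 0.7 and 0.9 are 16.4%, 14.3% and 10.9%.

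**3. The same trial with one pre-named comparison.** Any single time alone gives 4.7% to 5.3%. The area under the curve over 6–72 h gives 4.8% to 5.1%. Its trapezoid weights are 9, 21, 24 and 12, from intervals of 18, 24 and 24 hours.

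**4. The price of letting all four times count.** Bonferroni tests each time at 0.05 / 4 = 0.0125. At the difference that gives 85% power at 0.05, power at any one time falls to 67% (t-test) or 69% (normal approximation). Restoring 85% needs a total of about 58 or 56 patients respectively.

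**The case against.** The best defence is that this is an omission and not an error, and that a statistical analysis plan that is not shown may settle it. Part of that stands: test names, the detailed multiplicity procedure and the handling of secondary times are commonly left to such a plan. The time of the primary outcome is different. The protocol itself fixes the hypothesis, the alpha and the sample size, so it should say which comparison they refer to. If an analysis plan already names one, the protocol need only repeat it.

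The second defence is the planned test of change over time. It does not settle the matter: the test is unnamed, it is not said to compare the sealers (it could equally describe change within a group), and it is not called the deciding analysis.

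Three stronger readings are tempting, and the document supports none of them.
- A reader might infer that the trial will declare a difference if any time is significant. The protocol does not say so; it only fails to exclude it. The inflated rates are therefore conditional.
- A reader might infer that 40 patients is wrong or too few. The paragraph says "Sample size calculation was performed using G power (3.1.9.4) software, based on a previous study" without giving the effect size or SD. That is a separate gap in reporting and shows no error in the number.
- A reader might infer from the literature review, where "the severity starts to drop from the first day till less than 10% after 7 days", that power must fall at the later times. That statement concerns the overall level of pain. Power depends on the difference between sealers relative to its SD, and the document gives neither at any time.

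**Conclusion.** The point holds in limited form. The protocol tests one hypothesis at 0.05 on an outcome measured four times after treatment, and fixes neither the deciding time or summary nor a multiplicity rule. That follows from the text alone and needs no assumption.

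Its size depends on a decision rule that the protocol leaves open. If any time may count, the false-positive rate is roughly two to nearly four times the stated 5%: about 10% at a correlation of 0.9, up to 18.5% with independent times. The correlations are assumed. One pre-named comparison stays at about 5%. This is worth correcting because it is cheap; it does not show the design or the sample size to be wrong.

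**What to change.** Before outcome data are examined, add to the protocol:

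1. One primary between-group comparison, either VAS at one pre-chosen time or the area under the VAS curve over 6–72 h, tested at two-sided 0.05 with a named non-parametric test.
2. A statement that the other times and the change-over-time test are secondary.
3. Alternatively, if all four times are to count, a multiplicity adjustment such as Holm, or Bonferroni at 0.0125 per time.
4. A sentence tying the sample of 40 to the chosen comparison. If the inputs of the original calculation cannot be recovered, state what it detects: about 1.0 SD with a rank test at two-sided 0.05, reading 0.85 as power.

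The cost is a few sentences, with no added visits or data. An isolated significant result at a secondary time could no longer support the conclusion. The area under the curve loses power if a difference is short-lived, and it needs a rule for a missing score. The adjustment in item 3 lowers power at each time unless the sample is enlarged.

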Sadaf and Ahmad, ⁽¹⁴⁾ assessed postoperative pain and its associated clinical factors in endodontic therapy through a cross sectional study including one hundred and forty patients with premolars and molars requiring endodontic treatment and the treatment was performed in multiple visits. Results showed a significant difference in postoperative pain which was higher in females than males, mandibular teeth than maxillary teeth and in symptomatic than asymptomatic patients. There was no significant difference regarding tooth type, obturation length and sealer extrusion. So, gender, preoperative pain, maxillary, or mandibular teeth were considered risk factors affecting postoperative pain.

Mathew ⁽¹⁵⁾ reviewed and critically analyzed the influence of various factors on the incidence of postoperative pain.pain was evaluated through visual analogue scale (VAS) and facial gramice scale . A total of thirty-eight articles were included in the review, the articles were classified into variables affecting postoperative pain after endodontic treatment. Results showed high incidence of

postoperative pain in females, mandibular teeth, premolars when compared to anteriors, with positive correlation between preoperative and postoperative endodontic pain. Administration of premedication's (NSAIDs) decreases post operative pain. Step down instrumentation causes less debris extrusion and less pain. According to 13 different studies There was no significant difference between single or multiple visits. The effect of tooth vitality remained inconclusive.

Al-Rahabi ⁽¹⁶⁾ reviewed the effects of root canal treatment on postoperative pain and determined the possible predictive and related factors. Sixty-five studies were included in the review. Results showed a strong relationship existed between preoperative pain and postoperative pain, as well as high pain prevalence among women, mandibular and molar teeth. Application of intracanal medications may reduce the pain between visits. Moreover, recent advances in endodontics regarding magnification, instrumentation technique and alloy metallurgy in addition to activation of irrigant to reduce microbial load and disinfection for higher success rates of endodontic treatment reduced postoperative pain in terms of both intensity and duration. On the other hand, age of the patient and single or multiple visit root canal treatment showed no statistically significant differences.

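### The preoperative VAS is collected from every patient, but the stated between-group comparison of postoperative VAS does not use it, so some power may be lost

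*Protocol*

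**What the plan says.** Under the procedural steps of the Methods section, every patient is to "rate his /her pain level before endodontic treatment as preoperative reading on a visual analogue scale (VAS"). Under Methods of evaluation, the same scale is completed at 6, 24, 48 and 72 hours.

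Section G, Statistical analysis, then states: "Data will be statistically analyzed using non-parametric tests to compare numerical variables (age, VAS scores) amongst the groups". No test is named and no covariate is mentioned. The next sentence assigns a different, unnamed test to change in pain over time. The only factors to be correlated with postoperative pain are age and gender.

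The Review of Literature summarises one review "with positive correlation between preoperative and postoperative endodontic pain", and says of another: "Results showed a strong relationship existed between preoperative pain and postoperative pain". It gives no coefficient for either.

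**The concern.** The trial is small: 40 patients in two equal groups. The protocol's own literature section identifies preoperative pain as a predictor of the outcome and the Methods section measures it, but the stated group comparison leaves it out. VAS scores are listed beside age as variables to be compared between groups by the same kind of test, which reads as an unadjusted comparison.

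Adjusting for a prognostic baseline value removes outcome variation unrelated to the sealer and so raises power without more patients or data. What is at stake is precision. The validity of the comparison is not in question.

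**Working it through.** **Inputs from the protocol.** Total 40, equal groups, so 20 per group; alpha 0.05 (two-sided assumed); preoperative VAS collected; outcome at four time points.

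**Assumptions, because the protocol gives no figure.** The correlation r, the standardised difference d, and the share of zero scores. The value printed as beta, 0.85, is read as power.

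**The plan's own figure.** The total of 40 cannot be reproduced, because no effect size or SD is given. Solving backwards for 20 per group and 85% power, the normal formula gives d = (1.960 + 1.036)/√(20/2) = 2.996/3.162 = 0.948. The noncentral t gives d = 0.972.

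**Analytic check.** Adjustment multiplies the residual SD by √(1 − r²). Power then follows from a noncentral t on 37 df with noncentrality 0.972 × √10 / √(1 − r²). The equivalent unadjusted sample size is 40/(1 − r²).

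| r | 0 | 0.2 | 0.3 | 0.4 | 0.5 |
|---|---|---|---|---|---|
| Adjusted power, % | 84.9 | 86.3 | 88.1 | 90.4 | 93.3 |
| Equivalent unadjusted N | 40.0 | 41.7 | 44.0 | 47.6 | 53.3 |

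**Rank-based check by simulation.** Baseline and latent outcome are bivariate normal, 20 against 20, two-sided 5%, 20,000 runs per cell. The Mann-Whitney test (tie and continuity corrected) is compared with a rank ANCOVA: least squares of the ranked outcome on group and ranked baseline, with a t test on 37 df. To produce zeros, the outcome (SD 2 cm) is cut at 0 and rounded to 0.1 cm. Zeros are shown for the lower-pain group, then the other group. Entries are power in %.

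| d | Zeros | Mann-Whitney | ANCOVA r=0 | r=0.1 | r=0.2 | r=0.3 | r=0.4 | r=0.5 |
|---|---|---|---|---|---|---|---|---|
| 0.7 | none | 55.1–55.7 | 54.9 | 55.0 | 56.5 | 58.1 | 61.5 | 65.8 |
| 0.7 | 51% / 25% | 50.9–51.3 | 51.6 | 51.5 | 52.4 | 54.2 | 56.7 | 60.4 |
| 0.7 | 81% / 57% | 39.2–39.8 | 39.8 | 40.0 | 40.4 | 41.2 | 43.2 | 45.0 |
| 0.97 | none | 82.6–83.2 | 82.1 | 82.6 | 83.8 | 85.1 | 87.7 | 90.3 |
| 0.97 | 81% / 46% | 68.2–69.1 | 68.0 | 68.5 | 69.7 | 71.2 | 72.8 | 76.2 |

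Under the null, with these floors, type I error is 4.6–5.2% for Mann-Whitney and 4.7–5.4% for rank ANCOVA. Without the continuity correction, Mann-Whitney power under floors is 0.5–0.9 points higher, so the gains there are that much smaller.

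**Effect of the entry criteria.** Only "Patients with teeth diagnosed with symptomatic irreversible pulpitis" are enrolled, which may narrow the spread of preoperative VAS and lower r. If r is 0.5 in a mixed population and the baseline SD falls to a fraction u of its value there, then r′ = r·u/√(1 − r² + r²u²).

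- u = 0.5: r′ = 0.25/√0.8125 = 0.277
- u = 0.7: r′ = 0.35/√0.8725 = 0.375

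At d = 0.7 (40,000 runs per cell), the gains at these two values of r are 2.3 and 5.2 points with no floor, 2.5 and 5.0 with 51% zeros, and 1.7 and 3.3 with 81% zeros (1.1 and 2.5 without continuity correction).

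**Extreme floors.** At d = 0.7 and 92% / 77% zeros, rank ANCOVA against Mann-Whitney is 28.0% v 27.3% at r = 0.3 and 29.4% v 27.5% at r = 0.5. At 96% / 86% zeros it is 16.0% v 15.9% and 16.9% v 16.0%.

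**The case against.** **Choice of covariates is usually left to the SAP, and the protocol names no test.** A rank ANCOVA would not contradict the word non-parametric. That is fair, and an unseen SAP may already adjust. But the protocol does state how VAS will be compared, and it lists the factors to be related to pain without preoperative pain. The point is limited to that wording.

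**The test of change over time may use the preoperative reading.** It may. As written, it concerns change over time and not the group comparison. A change score would be no substitute: with equal variances its variance is 2(1 − r) times that of the raw score, for example 1.4 times at r = 0.3, so it loses precision whenever r is below 0.5.

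**Nothing in the document fixes r for this population.** This stands. Neither review's coefficient is given, and the text does not say whether the links are graded or merely contrast pain with no pain. A further cited study reports more pain in "mandibular teeth than maxillary teeth and in symptomatic than asymptomatic patients", and a single-visit cohort names the presence of preoperative pain as a predictor. Both mainly contrast presence with absence, a contrast the entry criteria largely remove, so neither is counted as support.

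**The gain may be small.** This also stands. At d = 0.97 with no floor it is about 1 point at r = 0.2 and 2 at r = 0.3. The literature section reports a 4% prevalence of postoperative pain in the single-visit cohort and, from a systematic review, that "the severity starts to drop from the first day till less than 10% after 7 days". Many zeros at later time points are therefore plausible. At 96% zeros the gain is about 0 to 1 point, with no material loss.

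**Conclusion.** The point holds as an inexpensive improvement. The stated comparison is valid under randomisation but makes no use of a baseline reading that the protocol collects and that its cited reviews link to the outcome.

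At d = 0.7 with few zeros, the expected change is from about -1 point of power at r = 0 to about +10 at r = 0.5. If eligibility restricts the baseline range as assumed above, the gain is about 2 to 5 points, and about 1 to 3 with 80% zeros. The largest loss, at r = 0, is about 1 point.

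These sizes rest on assumed values of r, d and the share of zeros, so the true gain is unknown and may be small. The recommendation rests on the imbalance between a possible gain of several points and a loss of about 1 point at worst.

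**What to change.** In section G, state that the between-group comparison of postoperative VAS at 6, 24, 48 and 72 hours is a rank-based ANCOVA:

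- rank the postoperative VAS and, separately, the preoperative VAS over both groups together, with mid-ranks for ties;
- regress the ranked outcome on group and ranked preoperative VAS;
- test the group term two-sided at 5%.

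Keep the unadjusted Mann-Whitney test at the same time points as a sensitivity analysis. Fix the choice before any outcome data are seen, so that adjustment cannot be selected on the results.

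The cost is analysis wording only. No patient, visit or measurement is added. One adjusted test replaces one unadjusted test at each time point, so the number of main tests is unchanged.

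### Gender is compared between the groups and correlated with pain but has no stated place in the sealer comparison, although the protocol cites it, like preoperative pain, as prognostic

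*Protocol*

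**What the plan says.** Section G-Statistical analysis of the protocol makes three statements that bear on this point.

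- On the outcome: "Data will be statistically analyzed using non-parametric tests to compare numerical variables (age, VAS scores) amongst the groups". No stratum or covariate is mentioned.
- On gender as a baseline variable: "Categorical variables (gender, type of teeth) will be compared amongst the groups". No test, threshold or consequence is given.
- On gender and pain: "the correlation assessments between age factor and postoperative pain, and gender factor and postoperative pain will be done".

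Section C-Patient allocation says "Using computer generated randomization, the participants will be allocated randomly into two equal groups" and mentions no stratification. Section A-Sample size determination says "The predicted sample size (n) is a total of 40", hence 20 per group. Procedural steps has each patient record a VAS score before treatment, but section G does not name that score as a covariate.

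The Review of Literature summarises four sources on predictors of postoperative pain, and each reports more pain in women.

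- The single-visit study of 1,328 patients names "presence of pre-operative pain, old age, gender (females recorded higher), and mandibular teeth".
- The summary of the cross-sectional study of 140 patients concludes: "So, gender, preoperative pain, maxillary, or mandibular teeth were considered risk factors affecting postoperative pain".
- The review of 38 articles reports a higher incidence in females and in mandibular teeth, and a positive correlation with preoperative pain.
- The review of 65 studies reports a strong relationship with preoperative pain, "as well as high pain prevalence among women, mandibular and molar teeth".

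The introduction also includes gender in its list of factors.

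**The concern.** The protocol treats gender as prognostic in its background and plans to relate it to pain. In the comparison that answers the trial's question, as section G describes it, gender plays no part.

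Comparing gender between the groups does not fill that gap. If the comparison is a significance test, its null hypothesis is true by design, because allocation is random. With 20 per group it would also have little chance of flagging an imbalance of practical size. Whatever it shows, the comparison leaves the sealer estimate unchanged. The correlation of gender with pain is a separate analysis and does not change the estimate either.

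Two things are at stake. One is a shift in the sealer difference, conditional on the gender split that happens to occur. The other is precision that an already recorded variable could provide. The same reasoning applies to the preoperative VAS, which the four sources support just as consistently.

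**Working it through.** **Inputs from the protocol.** Total 40 in two equal groups, so 20 per group; alpha 0.05. Not given: the expected share of women, the size of the gender effect on VAS, the VAS standard deviation and the target difference. The first two are assumed below, and results are in SD units.

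**The plan's own figure.** The total of 40 cannot be reproduced, because no difference or SD is stated. Solving backwards with a two-sided t-test at 0.05, and reading the stated beta of 0.85 as power, 20 per group corresponds to a standardised difference of about 0.97. This serves only as a yardstick.

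**Step 1: how often a chance imbalance arises.** Take the numbers of women as independent A, B ~ Binomial(20, π). At π = 0.5, A − B + 20 follows Binomial(40, 0.5), so

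- P(|A − B| ≥ 4) = 2 × P(Binomial(40, 0.5) ≤ 16) = 0.268 (a gap of at least 20 points);
- P(|A − B| ≥ 6) = 2 × P(Binomial(40, 0.5) ≤ 14) = 0.081 (a gap of at least 30 points).

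**Step 2: how often such a gap goes unflagged.** Enumerating all (A, B) and assuming a 0.05 threshold:

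| Share of women | Gap | Occurs | Occurs with chi-square p ≥ 0.05 | Occurs with Fisher p ≥ 0.05 |
|---|---|---|---|---|
| 50% | ≥ 20 points | 0.268 | 0.226 | 0.248 |
| 50% | ≥ 30 points | 0.081 | 0.038 | 0.060 |
| 60% | ≥ 20 points | 0.258 | 0.210 | 0.234 |
| 60% | ≥ 30 points | 0.075 | 0.026 | 0.051 |

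At 50% women, uncorrected chi-square misses 0.226/0.268 = 84% of gaps of 20 points or more, and Fisher misses more. For example, 7 v 13 women gives chi-square p = 0.058 and Fisher p = 0.113.

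**Step 3: what a gap does to the sealer difference.** Let g be the assumed gender effect in within-gender SDs and D the gap in the share of women. The shift is g × D. The standard error of the difference is √(2/20) = 0.316 SD. The type I error given that gap, by normal approximation, is 1 − Φ(1.96s − gD/0.316) + Φ(−1.96s − gD/0.316), with s = √(1 + g²(0.25 − D²/4)).

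For g = 0.5 and D = 0.3: the shift is 0.15, 0.15/0.316 = 0.474, s = 1.028 and 1.96s = 2.015. The error is then 0.0617 + 0.0064 = 0.068.

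| g | Shift, 20 points | Conditional type I error | Shift, 30 points | Conditional type I error |
|---|---|---|---|---|
| 0.3 | 0.06 | 0.052 | 0.09 | 0.057 |
| 0.5 | 0.10 | 0.054 | 0.15 | 0.068 |
| 0.8 | 0.16 | 0.059 | 0.24 | 0.092 |

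Against the yardstick of 0.97 SD, the shifts run from 0.06/0.97 = 6% to 0.24/0.97 = 25%. At a 10-point gap the conditional error is 0.041–0.049, just below nominal.

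**Step 4: precision.** With half the patients women, gender explains R² = 0.25g²/(1 + 0.25g²) of the variance: 0.022, 0.059 and 0.138 for g = 0.3, 0.5 and 0.8. Adjustment is worth about 40 × R² = 0.9, 2.4 and 5.5 patients, before the small cost of one degree of freedom.

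Steps 3 and 4 use mean differences and are approximate for a rank test.

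**The case against.** - **The unadjusted test is valid.** This stands. Over all randomisations the comparison is unbiased and keeps its error rate. A reader might infer that omitting gender biases the trial, but random allocation rules that out. The shift is conditional on the split obtained.
- **The protocol states no balance rule.** This also stands. A reader might infer that a non-significant gender comparison is to serve as a licence to ignore imbalance. Section G states no threshold and no such rule. The wording says only that gender is compared; a significance test is the natural reading, since the preceding sentences use the word for testing. Chi-square, Fisher and 0.05 in the working are assumptions.
- **A statistical analysis plan may add adjustment.** It may, and nothing in section G forbids a stratified rank test. The point is not that the protocol is silent: it gives gender two roles, neither of which can protect the sealer comparison.
- **Gender is not special.** This stands too. All four sources equally name preoperative pain and mandibular teeth, so a remedy for gender alone would be poorly justified when the preoperative VAS is recorded.
- **The effect is small.** Largely right. The frequent gaps (20 points or more, 27%) and the largest shifts (30 points, 8%) should not be run together. The protocol gives no gender effect on VAS, so a shift in centimetres cannot be derived from it.

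**Conclusion.** The point holds as a minor, free improvement. As section G stands, gender is compared between the groups and correlated with pain, but has no stated role in the sealer comparison, despite the protocol's own evidence that it is prognostic. Nothing is invalid or contradictory. What is given up is some precision, about 1 to 6 of the 40 patients for a gender effect of 0.3–0.8 SD, and protection against a shift of 0.06–0.24 SD when a 20–30 point gap arises.

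These sizes rest on 20 per group from the protocol, and on an assumed 50% share of women and an assumed gender effect. Changing the share to 60% barely moves the imbalance frequencies. The shift is proportional to the gender effect, so a small true effect would make it negligible.

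**What to change.** In section G-Statistical analysis:

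1. Present age, gender and type of teeth descriptively by group instead of testing them.
2. Prespecify that the sealer comparison of postoperative VAS accounts for gender and the preoperative VAS, whatever balance is observed. A rank-based covariance model or a proportional-odds model with these terms would do. For gender alone, a van Elteren test stratified by gender keeps the analysis non-parametric.

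The correlation of gender with pain can stay as a secondary description.

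The cost is a change of analysis wording and one or two degrees of freedom. Both variables are already collected, and no patients are added.
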